## 1.0 Objectives\*

1.1 The purpose of this study is to determine if activation training of the hip musculature affects muscle activation and frontal plane mechanics in healthy individuals.

Specific Aim 1: Determine whether performance on the forward step-down test (FSDT) changes after an eight-week home exercise program (HEP) focused on hip musculature activation in healthy individuals.

Specific Aim 2: Determine whether surface electromyography (sEMG) hip musculature changes following an eight-week HEP focused on hip musculature activation in healthy individuals.

Specific Aim 3: Determine whether a dose-response relationship exists between compliance on the HEP and changes in FSDT scores in healthy individuals.

Specific Aim 4: Determine whether a dose-response relationship exists between compliance on the HEP and sEMG changes in hip musculature activation in healthy individuals.

1.2 Specific Aim 1:

$H_0$ : There will be no significant change in FSDT scores after an eight-week hip musculature activation HEP in healthy individuals.

$H_1$ : There will be a significant change in FSDT scores after an eight-week hip musculature activation HEP in healthy individuals.

Specific Aim 2:

$H_0$ : There will be no significant change in sEMG data of hip musculature after an eight-week hip musculature activation HEP in healthy individuals.

$H_1$ : There will be a significant change in sEMG data of hip musculature after an eight-week hip musculature activation HEP in healthy individuals.

Specific Aim 3:

$H_0$ : There will be no significant dose-response relationship between HEP compliance and FSDT scores in healthy individuals.

$H_1$ : There will be a significant dose-response relationship between HEP compliance and the FSDT scores in healthy individuals.

Specific Aim 4:

H0: There will be no significant dose-response relationship between HEP compliance and sEMG data of hip musculature in healthy individuals.

H1: There will be a significant dose-response relationship between HEP compliance and sEMG data of hip musculature in healthy individuals.

## 2.0 Background\*

2.1 Over the past 10 years, there has been a shift in the literature regarding treatment for individuals with frontal plane abnormalities and altered lower extremity biomechanics, especially in the case of individuals with patellofemoral pain syndrome (PFPS). Originally, the treatment focused on the knee joint itself and strengthening the quadriceps musculature. Current literature suggests that the focus of treatment for individuals with PFPS should be on the proximal hip joint. There is evidence that pain is reduced in individuals with PFPS after hip and knee muscle strengthening compared with knee muscle strengthening alone. While it is necessary to rule out true tibiofemoral and patellofemoral joint issues in individuals with PFPS, it is important to not neglect the transverse and frontal plane movements of the hip and ankle joints. Women are more likely to suffer from PFPS syndrome because they have a lower rate of torque development in the hip extensors, leading to an earlier activation of the hip and knee extensors, emphasizing the importance of focusing treatment on the proximal hip joint and surrounding musculature. It is important to remember that the muscles of the lower extremity are all connected via the lumbo-pelvic hip complex, which is why the recent literature focuses on more proximal musculature rehabilitation while treating more distal pathologies.

Weakness of the hip abductors, external rotators, and extensors has been shown to lead to increased frontal and transverse plane motions at the hip. There is evidence to suggest that there are improvements in pain and overall function after a hip abductor and external rotation strengthening program. However, strength training has been unable to generate movement changes in women with PFP. In a case report on two separate patients with patellofemoral pain, muscle recruitment exercises, endurance training exercises, and core stability exercises were used to treat their pain, function, strength, gait, and biomechanical abnormalities. A combination of hip muscle activation and strengthening decreased the symptoms in these patients and improved their overall function, including stair navigation. In other areas of the body, activation training vs strength training has been compared to see what yields better outcomes. There is a current hole in the literature regarding whether activation

training alone of the hip musculature can alter frontal plane movements of the lower extremity. There is evidence to support that activation training of certain muscles may lead to better performances of the muscle during more advanced training programs. Increasing core activation during exercises focused on the hip musculature, such as clam shells, side-lying hip abduction, and prone hip extension, was shown to overall increase muscle activation of the LE. As for dosing of these exercises, one minute isometric holds have been shown to improve recruitment of the hip muscles during weight bearing activities. Hip muscle activation training is an area of treatment which needs more research to see the overall benefits, but it has been explored in core musculature, so we hope to examine if similar results will occur at the hip joint.

- 2.2 Our participants will execute the hip activation intervention via an 8 week home exercise program (HEP). This is the first study on this topic by the authors; however, two of the authors have previously published work using the FSDT as an outcome measure, using the same procedures for assessment as in this investigation. The study will evaluate the effects of a hip activation training program via HEP on the FSDT, as well as compliance measures of the HEP to analyze a dose-response predictive relationship.
- 2.3 The FSDT is a relevant outcome measure for people with altered frontal plane movements after an activation training program because activation training has been shown to alter corticomotor excitability of the gluteus maximus and hip biomechanics. The FSDT has been shown to assess neuromusculoskeletal control of the hip, because treating the proximal musculature has been shown to be beneficial for outcomes. Intrarater reliability has been established for the FSDT in individuals with PFPS and has been shown to relate to changes in pain levels. Interrater reliability for the FSDT has also been established with good agreement of the quality and distinguishing of movements between raters. Validity has been established for the use of the FSDT on individuals with altered frontal plane mechanics.

Compliance measurements of the intervention sessions and the amount of change in the dependent variable pre- and post-intervention have been shown as a reliable way to predict a dose-response relationship. In this study, the authors aim to analyze a dose-response predictive relationship between compliance of the intervention sessions and altered FSDT scores, as well as change in gluteus medius and maximus activation via sEMG data.

We are aiming to determine if a hip musculature activation training HEP has any affect on FSDT scores and sEMG measures of activation and to see how compliance affects the FSDT and muscle activation.

### **3.0 Inclusion and Exclusion Criteria\***

- 3.1 Screening will be done concurrently with the written informed consent process through a self-reported assessment.
- 3.2 Inclusion: Participants must be current first or second year Doctor of Physical Therapy (DPT) students in the School of Allied Health Professions (SAHP) at LSU Health Shreveport (LSUHS).  
Exclusion: current knee pain or pathology in the dominant leg, and women with known pregnancy.
- 3.3 Regarding the inclusion of persons at increased risk:
  - Adults unable to consent: excluded due to not meeting inclusion criteria
  - Individuals who are not yet adults (infants, children, teenagers): excluded because this is not our target population
  - Pregnant women: excluded due to creating greater than minimal risk
  - Prisoners: excluded due to not meeting our inclusion criteria

### **4.0 Study-Wide Number of Subjects\***

- 4.1 N/A, not multi-institutional.

### **5.0 Study-Wide Recruitment Methods\***

- 5.1 N/A, not multi-institutional
- 5.2 N/A, not multi-institutional
- 5.3 N/A, not multi-institutional

### **6.0 Multi-Site Research\***

- 6.1 N/A, not multi-institutional
- 6.2 N/A, not multi-institutional
- 6.3 N/A, not multi-institutional

### **7.0 Study Timelines\***

- 7.1 The duration of an individual subject's participation in the study is 220 minutes or 3.66 hours. It will take 30 minutes to measure and record anthropometrics, sEMG, FSDT, and teach the HEP. The FSDT and sEMG measurements will be taken again at the end of the intervention program. The HEP should take a maximum of 10 minutes a session, therefore 20 minutes total are allotted each week. The duration anticipated to enroll all study subjects is 15 minutes. The estimated completion date for the study is August 2023.

## **8.0 Study Endpoints\***

- 8.1 The primary and secondary study endpoints are the completion of data collection and intervention for all participants, which will be completed by May 2023.
- 8.2 Refer to 8.1.

## **9.0 Procedures Involved\***

- 9.1 The study will utilize a repeated-measures design, where all participants will perform the FSDT for assessment pre- and post-intervention via an HEP while sEMG data is being collected from the gluteus medius and gluteus maximus. All of the activities listed above will be performed on the dominant LE. The HEP will be a combination of hip musculature activation exercises used by previous researchers that show an increase in hip muscle recruitment. Core activation via a side plank will be added to the clam exercise and the side-lying hip abduction exercise. In this design the dependent variables are the scores on the FSDT pre- and post-HEP, sEMG pre-and post-HEP, and compliance with the HEP. The independent variable is the performance of the eight-week HEP. Two physical therapist students will perform the FSDT assessments and sEMG data collection (CH and MS). Two faculty members will also assist with data collection (DF and EM). Prior to data collection and assessments, the two students (CH and MS) will be educated by the primary investigator (DF), who is a board-certified orthopedic clinical specialist physical therapist with ten years of experience, on the FSDT protocol. Scoring guidelines of the FSDT will be reviewed according to the study by Park *et al* and practiced prior to data collection. The sEMG electrode placement will come from *The ABC of EMG*. The procedure for collection of the maximum volitional isometric contraction (MVIC) of the gluteus medius will follow the protocol used in a study by Harput *et al*. The MVIC of the gluteus maximus will follow the protocol used in a study by Selkowitz *et al*, with the knee flexed to 90° in prone. The same methodology will be used from [name] and [name] for scoring and reporting of the FSDT scores.
- 9.2 One investigator (CH) will inform one PT cohort in room 1-117 inside the SAHP at LSUHS via word of mouth. During this time, the investigators will obtain informed consent. If the required number of participants is not met (N = 35), the other investigator (MS) will recruit students from the other PT cohort via word-of- mouth about the investigation and obtain informed consent until the required number of participants are enrolled. Each participant will be given a random number to ensure patient confidentiality. After enrollment, each participant will sign up with their participant number for a time

to attend an initial data collection session in the rehabilitation faculty clinic and the motion analysis lab 2-217 in the SAHP at LSUHS. Participants will meet in the rehabilitation faculty clinic and age, sex, height, weight, BMI, and dominant lower extremity (LE) will be recorded by DF or EM. The dominant LE is defined as the leg that they usually use to kick a soccer ball. Participants will take the elevator to the second floor and report to 2-217 for sEMG and FSDT data collection. During this time, sEMG electrodes will be applied to the gluteus maximus and medius of the dominant leg, following the placement criteria from *The ABC of EMG* by EM (for female participants) or DF (for male participants) and an MVIC for each muscle will be performed and recorded, with resistance by CH. Participants will be instructed on the procedure for the FSDT by CH prior to completing the test. The FSDT consists of five consecutive repetitions of a forward step down from a 20cm step, with one score given for the whole set of five repetitions. The two student investigators (CH and MS) will both score and average the number between the two scores. sEMG data and FSDT scores will be collected before and after the 8 week HEP. After the initial FSDT is completed, the participant will be educated on the HEP and the compliance chart by MS. The HEP will be a combination of hip musculature activation exercises used by previous researchers that show an increase in hip muscle recruitment. Core activation via a side plank will be added to the clam exercise and the side-lying hip abduction exercise. The HEP consists of five hip activation exercises, clams, clams with trunk activation via side-plank, side-lying hip abduction, side-lying hip abduction with trunk activation via side-plank, and hydrants. The participants will perform isometric contractions of these exercises for up to one minute on the LE used for testing. Once the participant is able to hold all of these exercises for one minute without a break, the participant will advance to the next step, adding a yellow theraband and completing the same exercises. If the participant is able to isometrically hold these five exercises for one minute with a yellow theraband, the participant will progress to a red theraband and repeat the process of working towards one minute holds of each exercise. Each participant will demonstrate the exercises of the HEP to ensure proper form and be informed on the proper progression of the exercises. A compliance chart will be given to the participants to track every time they perform the HEP. Previous authors have used compliance charts to measure this variable in preparation for a dose-response analysis for activation programs. The participants will take home their HEP, a compliance chart, and a yellow and red theraband. The participants will complete the HEP two days a week for eight weeks, with at least two rest days between sessions, and document the completion of the session on the compliance chart. At the end of the 8 week period,

each participant will be scheduled to return to the motion analysis lab to turn in their compliance sheet and perform a follow-up sEMG and FSDT using the same procedures as before.

9.3 Table of events that lists each procedure or test and how often the procedure or test will occur:

Written informed consent	1
Eligibility screening	1
Anthropometric assessment (height, weight, BMI)	1
FSDT	2
sEMG	2
HEP education	1
Compliance chart education	1
HEP	16
Compliance chart documentation	16

9.4 To reduce the risk of loss of confidentiality, participants will be assigned numbers. All hardcopy data will be stored in DF office (locked), room 2-234 in the SAHP at LSUHS in a locked drawer. All electronic data will be stored using Sharepoint connected to school email addresses with a password.

To reduce the risk of muscle soreness, participants will be educated on proper performance of the exercises, to space sessions at least two days apart, and to add a band or progress to a yellow theraband once they can perform all exercises for one consecutive minute on the dominant LE. An informed consent document with participant identification numbers will be used to obtain consent from the participants. A participant identification number key will be made to match the participant name to their assigned number to maintain confidentiality. A sign up for the anthropometric data collection and pre- and post-HEP sEMG and FSDT data collection will be created, allowing the participants to sign up with their identification number. An excel sheet to collect data will be used by the investigators. A compliance chart for the participants to track their exercise sessions will be created. A paper copy of the HEP will be given to the participants.

9.5 Data collected will consist of participant age, height, weight, BMI, all at the first visit, in addition to the following pre- and post-intervention: FSDT, sEMG from gluteus medius and maximus, recorded FSDT video. The data from the compliance chart will only be collected post-intervention.

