11.3 See 9.4

11.4 The student investigators (CH and MS) will be educated on the proper procedures of the FSDT, sEMG data collection, and the HEP by the primary investigator (DF) and co-investigator (EM). The FSDT will be analyzed and scored by the two student investigators (CH and MS). The student investigators (CH and MS) will record and average their scores following the completion of five repetitions to improve the quality of the data. The sEMG electrodes will be placed on the female participants by EM and on the male participants by DF. CH will provide the pressure for the MVIC and explain the FSDT procedure to every participant. MS will explain the HEP and the compliance chart to the participants. The primary investigator (DF) is a board-certified orthopedic physical therapist with 10 years of experience, who has published research on this test. The co-investigator (EM) is also a board-certified orthopedic physical therapist with 5 years of experience, who also published research on this test with the primary investigator.

11.5 The data that will be collected during the entire study includes: participant number, height, weight, BMI, sex, leg dominance, FSDT pre and post HEP, recorded FSDT video, sEMG from gluteus medius and maximus on the dominant leg during FSDT pre and post HEP, and compliance. Data storage will follow the guidelines in section 9.4. The data will be stored for the duration of the study and throughout the following semester while analyzing and finalizing data for presentation. The data will be kept up to one year after the completion of the data analysis in event that the research wants to be continued. The only people to have access to this information will be the primary investigators, student investigators, and the co-investigator (DF, EM, CH, MS). All investigators are responsible for the receipt and transmission of the data. Data will be manually transported to DF office room 2-234 in the SAHP at LSUHS. Electronic data will remain on Sharepoint.

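### The two student raters of the FSDT have no agreement level to reach before baseline and no stated use of the video, so scoring drift shared by both could not be told apart from a training effect in Aim 1

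*Combined protocol and SAP*

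**What the plan says.** - **Who scores.** Sections 9.2 and 11.4 give all FSDT scoring to the two student investigators. One score covers the set of five step-downs.
- **Preparation.** Under 9.1 the primary investigator teaches them the test, and published scoring guidelines are reviewed "and practiced prior to data collection". Sections 11.4 and 20.1 add the co-investigator as a trainer. No agreement statistic or pass mark is given.
- **Combining scores.** The students "will both score and average the number between the two scores" (9.2). Section 11.4 says that they "will record and average their scores following the completion of five repetitions to improve the quality of the data".
- **Follow-up.** The post-test repeats the baseline procedures (end of 9.2).
- **Video.** Sections 9.5 and 11.5 list a recorded FSDT video among the data, at both visits. No section says that it will be scored or used to check scores. The timing in 11.4 suggests live scoring, though the plan does not say so outright.
- **Reliability.** Section 2.3 relies on published work: "Interrater reliability for the FSDT has also been established with good agreement of the quality and distinguishing of movements between raters". It also says: "Intrarater reliability has been established for the FSDT in individuals with PFPS". Section 11.4 attributes one of the cited interrater studies to the two faculty investigators.
- **Design and test.** One group is measured before and after eight weeks (9.1), with a Wilcoxon signed-rank test on the FSDT (11.1).

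**The concern.** The Aim 1 result is the change in a score that depends on two people's judgement. Within each participant, the baseline rating always comes before the post rating, by about eight weeks. In between, the students go on rating other participants. If they become stricter or more lenient as they gain experience, the change lines up with visit. There is no control group in which the same drift would appear and be subtracted.

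The two students share their trainers and watch the same performances, so a common drift is plausible. It is also the kind of drift against which averaging gives no protection. Concealing compliance or visit from a live rater would not remove it either, since a masked rater can still drift over calendar time. At stake is whether a significant Aim 1 result can be read as a change in movement rather than a change in scoring.

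**Working it through.** **Inputs.** From 11.2: r = .27, d = .56, two-sided alpha .05, power .80, N = 29, 20% attrition, 35 recruited. From 11.1: Wilcoxon signed-rank test. Drift and rater error are not in the documents, so every value used for them below is assumed.

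**1. The plan's own sample size.**
- d = 2r/√(1 − r²) = 0.54/√(1 − 0.0729) = 0.561, given as .56.
- Wilcoxon power is approximated by the noncentral t with the sample multiplied by 3/π = 0.955.
- At N = 29 the effective n is 27.69, the noncentrality is 0.56 × √27.69 = 2.947 and the critical t is 2.053. Power is 0.810.
- At N = 28 power is 0.796, so 29 is reproduced.
- 29 × 1.2 = 34.8, hence 35 recruited. A 20% loss from 35 leaves 35 × 0.8 = 28 completers.

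**2. What the safeguards remove.** Let δ₁ and δ₂ be the change in each rater's severity from baseline to post. The change in the averaged score is then the true change + (δ₁ + δ₂)/2.
- Constant severity (δ₁ = δ₂ = 0): no bias.
- One rater drifts by δ: bias δ/2.
- Both drift by δ: bias δ, with no reduction.

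**3. False positives with no true effect.** Let s be the shift in the averaged score, in SDs of the pre-post change. With 28 completers the effective n is 28 × 0.955 = 26.74, the noncentrality is s√26.74 and the critical t is 2.057.

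| Assumed s | Noncentrality | Wilcoxon (approx.) | Paired t as cross-check |
|---|---|---|---|
| 0 | 0 | 5.0% | 5.0% |
| 0.1 | 0.517 | 7.9% | 8.0% |
| 0.2 | 1.034 | 16.9% | 17.5% |
| 0.3 | 1.551 | 32.1% | 33.4% |

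**4. Shared against one-rater drift, in points.** This simulation with the Wilcoxon test at n = 29 assumes an integer 0–6 scale, true-score SD 1.0, occasion SD 0.5 and rater-error SD 0.6.

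| Assumed drift | Both raters | One rater only |
|---|---|---|
| 0 | about 5% | about 4–5% |
| 0.25 point | about 25% | about 10% |
| 0.5 point | about 75% | about 24% |

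Before rounding, the SD of the change under these assumptions is √(2 × 0.25 + 2 × 0.36/2) = √0.86 = 0.93. A shared drift of 0.25 point is therefore about 0.27 SD, and its 25% falls between the 0.2 and 0.3 rows of step 3.

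**The case against.** The plan has more protection than a quick reading suggests: teaching by experienced investigators, published guidelines, practice, the same two raters and procedures at both visits, averaging, and video at both visits. Averaging is itself a fixed rule for unequal scores, and a mean that neither rater gave is no defect. Section 11.4 reads naturally as recording two scores per test, so agreement could be computed later. Section 9.1 also adopts the scoring method of the faculty investigators' published study, which may contain rules that cannot be seen here. All of this stands. What remains is that none of it is a stated check on agreement or drift, and agreement in a published study would not show that these two students agree.

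Stronger readings that a reader might infer, and that the documents do not support:
- **Drift will occur, or Aim 1 is biased.** Nothing in the documents shows drift, its size or its direction. The number of ratings between visits is limited by 35 participants, and the plan does not say how baseline and post sessions overlap.
- **The cited reliability belongs to other raters.** This is a reasonable inference. The documents say who published the study, not who rated in it. It is clear, though, that the intrarater evidence concerns people with patellofemoral pain, whereas this study excludes current knee pain in the tested leg.
- **Power is below that planned because the students agree poorly.** No agreement coefficient is given, either for them or behind d = .56, so any power loss would follow from chosen values.

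A further fair objection is that a threshold on a few recordings is crude. With two raters, an observed intraclass correlation of .75 has a 95% interval of about .27 to .93 on 10 recordings and .40 to .91 on 15. A pre-baseline check can catch gross disagreement but cannot certify reliability, which is why it should not be the only step.

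**Conclusion.** The concern holds as a conditional weakness in the design. It is not an error or a contradiction in the plan. As written, the plan sets no agreement level before baseline and commits to no check that would show drift shared by both raters, and the one-group comparison cannot separate such drift from a training effect.

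The size is illustrative: about 8%, 17% and 32% false positives at assumed shifts of 0.1, 0.2 and 0.3 SD of the change in the averaged score, with 28 completers and no true effect. If only one rater drifts, the shift in the average is half that rater's drift and the risk is much lower. The planned N of 29 is reproduced and is not affected.

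The point bears on Aim 1. A shift equal for all participants would not by itself create an association with compliance in Aim 3. The change is worth making because it is cheap and because calibration before baseline cannot be recovered once scoring has begun.

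**What to change.** Amend 9.1, 9.2 and 11.4 as follows.

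1. **Before the first baseline test**, both students independently score the same practice recordings against the primary investigator's scores. They continue practising until a preset agreement level (weighted kappa or intraclass correlation) is reached. State the level and the number of recordings.
2. **Keep both individual scores** for every test, and report inter-rater agreement by visit with the Aim 1 result.
3. **After all post-tests**, the same two students independently score the recorded pre and post videos in random order with visit concealed. State in advance whether this score is used for Aim 1 or reported alongside the live score. Any drift during this scoring is then no longer tied to visit.

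Step 3 is preferable to re-scoring practice recordings mid-study and re-training if the mean has moved. Suppose the limit were 0.25 point on 10 to 15 recordings, with an assumed rater-error SD of 0.6. The standard error of one rater's mean shift is 0.6 × √(2/10) = 0.27 to 0.6 × √(2/15) = 0.22, and for the two-rater mean it is 0.19 to 0.15. With no drift, the limit would be crossed 25–35% of the time for a single rater and 11–19% for the two-rater mean. A true shift of 0.25 would be missed about half the time. Re-training between visits could also itself create a shift aligned with visit.

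**Cost.** A few hours of scoring by existing staff, a small number of practice recordings (the plan mentions none, so someone must be filmed), and possibly a short delay before baseline. No extra participant visits are needed. One limit remains: the students may recall a live performance when they see the video, so concealment of visit may be imperfect.
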